Overview: We will enroll up to 30 Veterans and assess feasibility, acceptability, and preliminary efficacy of ME-CCT-A via telehealth. Veterans will receive ME-CCT-A via telehealth and undergo two study evaluations (baseline and 8 weeks) while also continuing with their usual medical, psychiatric, psychotherapeutic, and/or substance use treatment. Feasibility will be assessed by examining data on recruitment and retention rates, rate of completion of the intervention, and feasibility of testing procedures and data collection methods. Acceptability will be assessed through feedback surveys after study completion. We will assess the preliminary efficacy of ME-CCT-A on objective cognitive performance, daily functioning, subjective cognitive complaints, and psychiatric and substance use outcomes.

Intervention: Once at least 4 eligible Veterans have completed baseline visits, the 8-week group will begin via telehealth. The virtual group will be held through VA Video Connect or another VA-approved video meeting tool. Group sessions will last for 2 hours and consist of interactive didactic information and discussion and activities that introduce a variety of cognitive strategies and external aids. [name] (Co-PI) and/or another study staff member will run the CCT groups. Intervention materials will be mailed to participants prior to group start date. Attendance of each Veteran at each session will be noted. Individual make-up sessions will be offered to Veterans who miss a session, and attendance at make-ups will be recorded.

ME-CCT-A Treatment Manual: The structure of the intervention is determined by the ME-CCT-A treatment manual, which has been tailored to each cognitive domain commonly affected by SUDs (Huckans et al., 2018). Session materials correspond to compensatory cognitive training for difficulties with learning, memory, processing speed, executive functioning (multitasking abilities), verbal functioning, concentration, and attention.

Additionally, session content in the updated manual is tailored to address other symptoms related to SUDs that might be influencing cognitive functioning and incorporates motivational interviewing methods. Table 1 outlines the structure and content of the ME-CCT-A treatment manual and group sessions.

[figure not shown]

Table 1. ME-CCT-A Session Content

Session	Major Concepts	Examples of Strategies	Session Activities	Home Exercise

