Client Satisfaction Questionnaire (CSQ-8)	Satisfaction with the intervention (follow-up only)
Timeline Followback (TLFB)	Alcohol and cannabis consumption over a given time period
Alcohol Use Disorders Identification Test (AUDIT-C)	Alcohol use

ANALYTIC PLAN.

All data analyses will be conducted by study personnel with expertise in statistics, using Excel, SPSS, or other statistical software approved by the VA.

Phase 2, Aim 2 Feasibility and Acceptability: Descriptive statistics will characterize the feasibility of recruiting and retaining Veterans. Recruitment will be deemed feasible if we successfully screen for eligibility 50% of Veterans referred to the study and enroll 75% of screened Veterans who meet all study inclusion criteria. Retention will be deemed successful if we achieve 75% completion for post-treatment assessments. Chi-square tests of association and t-tests will compare demographic and clinical characteristics of successfully versus unsuccessfully recruited and retained Veterans to identify characteristics of Veterans who may require more intensive recruitment or retention efforts in a future trial. Acceptability will be assessed through surveys on treatment satisfaction (i.e., CSQ-8 with additional study-specific items) following group completion. Treatment will be deemed acceptable if $\geq 70\%$ of Veterans score ≥ 24 on the CSQ-8.

Phase 2, Aim 3 Preliminary Efficacy: Descriptive statistics and exploratory analyses will be used to assess the normality of the data and homogeneity of variance. Although our small sample size will limit our power to detect significant differences between pre- and post-treatment measures, we will

conduct preliminary analyses using t-tests to examine whether pre-post changes are in the expected directions. We will examine effect size (Cohen's d) and significance of our measures.

Study Population

See sponsor/3rd party protocol for requested information in this section. Indicate what heading/subheading in the 3rd party protocol that the information is located:

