The proposed study is conducted at a single site. We propose to enroll up to 30 Veterans in this pilot trial. Because our primary purposes are to examine feasibility and acceptability to Veterans with AUD, achieving adequate statistical power is not a primary concern of this pilot clinical trial. Results from this study with a sample size of up to 30, combined with comparisons to similar studies of CCT with other Veteran groups (e.g., those with mild TBI history), will provide adequate information on expected effect size to allow for estimations of statistical power for a future proposal of a larger pilot trial.

Inclusion criteria include: 1) Male and female Veterans (>18 years) who meet criteria for AUD in early remission (>1 month, <12 months remission) based on the DSM-5 (American Psychiatric Association, 2013); 2) Concern about a mild cognitive decline that has been identified by the Veteran or a knowledgeable informant (e.g., SUD treatment providers), and the Veteran wants treatment for their cognitive concerns; and 3) Access to internet and webcam.

Exclusion criteria include: 1) Intoxication or impaired capacity to understand study risks and benefits; 2) Major Neurocognitive Disorder, dementia, or neurodegenerative disorder (e.g., Alzheimer's Disease); and/or 3) Auditory or visual impairments that would prevent ability to participate in the cognitive rehabilitation group or benefit from compensatory strategies.

Eligibility will be established by electronic medical record review and will be confirmed by the Veteran during the initial phone call.

1. VA-SPECIFIC REQUIREMENT (inclusion of non-Veterans):

N/A. The study does not include non-Veterans.

See sponsor/3rd party protocol for requested information in this section. Indicate what heading/subheading in the 3rd party protocol that the information is located:

Subject Identification/Recruitment

See sponsor/3rd party protocol for requested information in this section. Indicate what heading/subheading in the 3rd party protocol that the information is located:

Recruitment, eligibility screening, consenting, study visits, and CCT groups will be conducted by approved clinical research staff. A Waiver of Authorization and Informed Consent Process for Screening/Recruitment Purposes will be obtained to facilitate subject identification and recruitment.

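### With at most 30 enrolled and the 75% retention bar met, no more than 7 Veterans are lost, so the planned chi-square and t-tests cannot reliably identify who needs more retention effort; report differences with intervals instead.

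*Combined protocol and SAP*

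**What the plan says.** Three statements in the combined protocol and SAP fix the size of this comparison and its purpose.

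- **Size.** Research Design and Methods, Overview: "We will enroll up to 30 Veterans". Study Population repeats the figure, which is a ceiling.
- **Retention bar.** Analytic Plan, feasibility and acceptability paragraph: "Retention will be deemed successful if we achieve 75% completion for post-treatment assessments".
- **Tests and purpose.** Same paragraph: "Chi-square tests of association and t-tests will compare demographic and clinical characteristics of successfully versus unsuccessfully recruited and retained Veterans", the purpose being "to identify characteristics of Veterans who may require more intensive recruitment or retention efforts in a future trial".

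Two further statements bear on how much the tests are expected to show. Study Population says that "achieving adequate statistical power is not a primary concern of this pilot clinical trial". The preliminary-efficacy paragraph of the Analytic Plan carries its own caveat, "Although our small sample size will limit our power to detect significant differences between pre- and post-treatment measures", and then adds: "We will examine effect size (Cohen's d) and significance of our measures".

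For the retained-versus-lost comparison, the plan gives no significance level, list of characteristics, effect estimate, confidence interval, small-count test or multiplicity rule.

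**The concern.** The comparison is meant to inform the retention plan of a later trial, yet one of its two groups is very small whenever the trial meets its own retention bar. Chi-square and t-tests are the only tools named for it. With so few lost, a moderate predictor of dropout will usually give a non-significant result, and without an estimate and interval beside it such a result is easily taken to mean that the groups do not differ. If many characteristics are compared, some may also reach significance by chance. The problem grows as retention improves, because the lost group shrinks further.

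What is at stake is the usefulness of this comparison for the next trial. No feasibility or acceptability criterion of this trial depends on it.

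**Working it through.** **Inputs from the documents:** at most 30 enrolled; retention bar 75%. The plan states no power or detectable difference for this comparison, so there is no figure to reproduce.

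**Assumptions:** two-sided level 0.05, unadjusted; standardized differences d of 0.5 to 1.25; 80% power as a benchmark only; 10 to 15 characteristics, treated as independent.

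**1. Group sizes.** 0.75 × 30 = 22.5, so at least 23 must be retained and at most 30 − 23 = 7 are lost. With fewer enrolled and the bar met, the lost group is 7 or smaller.

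**2. t-test, 23 against 7.** The standard error in SD units is √(1/23 + 1/7) = 0.432. With 28 degrees of freedom the critical value is 2.048, and the noncentrality is d / 0.432. Power from the noncentral t distribution:

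| d | Noncentrality | Power |
|---|---|---|
| 0.5 | 1.16 | 20% |
| 0.8 | 1.85 | 43% |
| 1.0 | 2.32 | 61% |
| 1.25 | 2.90 | 80% |

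The 95% interval for a mean difference has half-width 2.048 × 0.432 = 0.88 SD.

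**3. Other splits, at d = 0.8.** Better retention lowers power: 27 against 3 gives 25%. Missing the bar helps only a little: 20 against 10 gives 51%, and an even 15 against 15 gives 56%. Fewer enrolled is worse: 15 against 5 gives 31%. For scale, at 25% loss, 80% power needs about 68 enrolled (17 lost) for d = 0.8 and about 172 (43 lost) for d = 0.5.

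**4. Expected counts for a yes/no trait.** If a proportion p of all 30 have the trait, the expected counts among the lost are 7p and 7(1 − p). The smaller is largest at p = 0.5, where it is 3.5. At p = 0.3 it is 2.1, and at p = 0.2 it is 1.4. A count of 5 needs L/2 ≥ 5, so L ≥ 10 lost. That is retention of at most 20/30 = 66.7%, which fails the bar.

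**5. Power for a yes/no trait, 23 against 7.** By exact enumeration of two binomials at level 0.05:

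| Retained v lost | Pearson chi-square | Fisher exact |
|---|---|---|
| 50% v 70% | 17% | 8% |
| 50% v 80% | 32% | 18% |
| 30% v 60% | 31% | 22% |
| 30% v 70% | 49% | 37% |

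If 20% of the retained have the trait, chi-square reaches 80% power only when about 75% of the lost do.

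**6. Chance findings.** With k independent tests and no true difference, the chance of at least one result below 0.05 is 1 − 0.95^k. For k = 10 this is 40%, and for k = 15 it is 54%. Correlation between characteristics would lower both.

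**The case against.** The strongest reply is that the protocol has already conceded the point. Study Population says that adequate power is not a primary concern, and that sentence covers the whole pilot. The aim is also worded tentatively, since it speaks of Veterans who may need more effort, and the comparison feeds no success criterion. This stands, and it limits the weight of the point. It does not dispose of it: the Analytic Plan's specific caveat and its promise of effect sizes are tied to the pre-post measures, and a general remark on power does not address the expected counts.

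Four stronger readings are tempting, and the documents do not support them.

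- **A reader might infer that the tests can find nothing.** Very large differences, with d of about 1.25 or more, would be found with 80% power.
- **A reader might infer that a significance threshold alone will decide which characteristics are carried forward.** The plan states no such rule, and the same paragraph begins with descriptive statistics for recruitment and retention.
- **A reader might infer that chi-square gives badly inflated false-positive rates here.** By enumeration at 23 against 7, for trait prevalences of 5% to 50%, its actual type I error runs from 1.6% to 5.7%, so it is mostly conservative. The small counts make the approximation unreliable, but they do not make it grossly liberal.
- **A reader might extend the point to recruited against not recruited Veterans.** That half of the sentence is not capped at 30. If 30 enrol and they are exactly 75% of eligible screened Veterans, the split is 30 against 10, with 57% power at d = 0.8.

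**Conclusion.** The point holds for the retained-versus-lost comparison. With the retention bar met and no more than 30 enrolled, the lost group is 7 or fewer, t-test power is about 20% at d = 0.5 and 43% at d = 0.8, and the usual chi-square count condition cannot be met for any yes/no trait. The tests cannot reliably identify the characteristics that they are meant to identify.

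The group sizes and expected counts follow from the plan's own figures. The power figures rest on the assumed two-sided 0.05 and the assumed effect sizes. The 40% to 54% chance of a false lead rests on an assumed number of characteristics and on independence, so it is an illustration only. The conclusion about moderate differences does not depend on the exact split, because even 15 against 15 gives only 56% power at d = 0.8.

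This is an inexpensive improvement to a secondary analysis. It casts no doubt on the retention, recruitment or acceptability criteria.

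**What to change.** In the feasibility and acceptability paragraph of the Analytic Plan, for retained versus lost Veterans only:

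- Make the primary output a side-by-side table giving, for each characteristic, the mean or risk difference and its 95% confidence interval.
- Label the comparison exploratory, and treat any difference as a lead for the next trial.
- State that a wide interval or a non-significant test is not evidence of no difference.
- If a p-value is also given for a categorical trait with expected counts below 5, use an exact test.

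Listing the characteristics in advance would also let a reader judge how many chance leads to expect.

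**Cost:** a few sentences and no new data. The downsides are that no characteristic is declared significant, and that an exact test is more conservative than chi-square (for 30% v 70%, 37% power against 49%).

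### Do the pre-post t-tests need to allow for Veterans being treated together in groups?

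*Combined protocol and SAP*

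**What the plan says.** Under Research Design and Methods (Intervention), treatment is delivered in groups: "Once at least 4 eligible Veterans have completed baseline visits, the 8-week group will begin via telehealth". The sessions are shared and interactive: "Group sessions will last for 2 hours and consist of interactive didactic information and discussion". The same paragraph refers to groups in the plural, but gives neither their number nor a maximum size. It also says "Attendance of each Veteran at each session will be noted" and "Individual make-up sessions will be offered to Veterans who miss a session".

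The Study Population section sets the size: "We propose to enroll up to 30 Veterans in this pilot trial". There is one arm.

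For efficacy, the Analytic Plan will "conduct preliminary analyses using t-tests to examine whether pre-post changes are in the expected directions", and adds: "We will examine effect size (Cohen's d) and significance of our measures". It has no term for group or facilitator and names no ICC, confidence interval, significance level or efficacy decision rule. It does warn that the small sample limits power.

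The Study Population section says the results "will provide adequate information on expected effect size to allow for estimations of statistical power for a future proposal of a larger pilot trial". The subject of that sentence is this study's results taken together with comparisons to similar CCT studies in other Veteran groups, not this study's results alone.

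**The concern.** Veterans in one group share sessions, discussion, a facilitator and a calendar period, so their changes may be correlated. A paired t-test assumes independent changes. With positive correlation its standard error is too small. P-values are then too small on average, and any interval later placed around the mean change or Cohen's d is too narrow.

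The plan's own caution about small samples concerns missed effects. It does not warn of the opposite error, excess false positives and overstated precision. Because the effect sizes are meant to help power a later trial, a planner could take d to be better determined than it is.

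**Working it through.** The plan states no power, significance level or sample-size calculation, so there is no figure to reproduce. The check asks how far the planned test could be off.

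**Inputs from the documents**
- Enrolment of up to 30 (Study Population).
- At least 4 Veterans to start a group (Intervention). If every group meets this, 30/4 = 7.5, so at most 7 groups.
- Retention target of 75% (Analytic Plan): 0.75 × 30 = 22.5, taken as 23 completers.

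**Assumed inputs**
- Two-sided 5% level and normally distributed changes.
- ICC from 0 to 0.10.
- Completers per group: 4,4,3,3,3,3,3 (seven groups), 5,5,5,4,4 (five) or 8,8,7 (three).

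**Step 1: standard error.** The design effect is 1 + (Σm²/Σm − 1) × ICC, and the standard error is understated by about its square root. At ICC 0.05:
- Seven groups: Σm² = 77, so 1 + (77/23 − 1) × 0.05 = 1.117; square root 1.06.
- Five groups: Σm² = 107, so 1 + (107/23 − 1) × 0.05 = 1.183; square root 1.09.
- Three groups: Σm² = 177, so 1 + (177/23 − 1) × 0.05 = 1.335; square root 1.16.

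**Step 2: false-positive rate of the planned t-test** (exact calculation, confirmed by simulation)

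| Groups | ICC 0 | 0.01 | 0.05 | 0.10 |
|---|---|---|---|---|
| Seven | 5.0% | 5.3% | 6.3% | 7.7% |
| Five | 5.0% | 5.4% | 7.1% | 9.3% |
| Three | 5.0% | 5.7% | 8.9% | 12.9% |

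With all 30 retained in three groups of 10, the rate reaches 15.5% at ICC 0.10.

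**Step 3: the effect size.** At a true d of 0.5, the median estimate is 0.51 (0.52 with three groups at ICC 0.10). Its sampling SD rises from 0.23 at ICC 0 to 0.26 / 0.27 / 0.30 at ICC 0.10 (seven / five / three groups). A nominal 95% interval for d that ignored group would cover 93.8 / 93.1 / 91.5% at ICC 0.05, though the plan names no such interval.

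**Step 4: the remedy.** A one-sample t-test on the group mean changes restores a 5.0% false-positive rate for near-equal groups, but leaves 6, 4 or 2 degrees of freedom. At d = 0.5:

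| Groups | Power, ICC 0 | Power, ICC 0.05 | Power, ICC 0.10 |
|---|---|---|---|
| Seven | 52% | 47% | 44% |
| Five | 45% | 39% | 35% |
| Three | 28% | 23% | 20% |

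The planned t-test has 63% power at ICC 0. With no clustering at all and d = 0.5, among trials where the planned test is significant, the group-mean test is not significant in about 24% / 36% / 61% (seven / five / three groups). Estimating the ICC does not help either: at a true value of 0.05, the median 95% interval is −0.18 to 0.64 with five groups and −0.11 to 0.83 with three.

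**Step 5: what the p-values can support in any case.** The battery has 16 instruments or subtests measured before and after: eight NAB subtests, D-KEFS, BAM, PRMQ, PCSS, two PROMIS forms, TLFB and AUDIT-C. No multiplicity control is planned. If the tests were independent (an assumption), the chance of at least one false positive at ICC 0 would be 1 − 0.95^16 = 56%. Clustering would add to this, but these p-values could not be read as confirmatory even without it.

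**The case for a change.** The case for acting is that the statistical point is correct, efficacy is a stated aim, and significance will be examined. The plan's caveats do not mention overstated precision. A short caveat, the number and sizes of groups and a sensitivity test need no new data and run in the software the plan names. The assumption of 23 completers does not exaggerate the problem, since full retention makes the inflation larger.

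Much of this stands. Independence is assumed without comment, and the test is anti-conservative under any positive ICC.

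The call for a change does not stand. The caveat and the group counts alter no estimate or test; they belong in the report, and an analyst can supply them from the attendance records. The group-mean test would alter what is shown, but it is a poor trade: it would be repeated over at least 16 measures, more if multi-domain instruments are scored by domain, and a non-significant result would say almost nothing. If fewer than three groups run, which enrolment of up to 30 allows, it is of no practical use: two groups leave one degree of freedom and 15% power at ICC 0.

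**Conclusion.** The observation is right, but no change to the plan follows. The tests are there to see whether changes run in the expected direction, and clustering leaves direction and the typical d essentially intact. No decision rule rests on their p-values; feasibility and acceptability, the primary purposes, are judged by separate percentages.

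Under the assumptions above, the false-positive rate moves from 5% to 6.3 to 8.9% at ICC 0.05, and hardly at all at 0.01. Manualized content, a single site and individual make-up sessions could keep the ICC low, though the documents give no value. The least favourable case at 23 completers, three groups and ICC 0.10, gives 12.9%; that would matter for a confirmatory test but not for an exploratory one. The effect size is to be read alongside other CCT studies, which limits the harm from its overstated precision. The available correction costs more in power and apparent contradictions than it returns.

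This would need revisiting if an efficacy p-value were given a decision role, or if this trial's d alone were used to size the next one.
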